## 4.2 Scientific rationale for study design

Leucine-rich glioma inactivated 1 is a protein mainly expressed in the hippocampus and the temporal cortex, where it is secreted into the synaptic space. It is part of an inhibitory pathway

linking the presynaptic voltage-gated potassium channel complex and the postsynaptic  $\alpha$ -amino-3-hydroxy-5-methyl-4-isoxazolepropionic acid (AMPA) receptor (Fukata et al, 2010; Ohkawa et al, 2013). Specifically, it is classified as an antineuronal surface antigen or antisynaptic protein-associated AIE. Kornau et al (2020) have recently demonstrated that LGI1 antibodies alone are sufficient to promote neuronal excitability, a basis of seizure generation. Seven of the overall 26 LGI1 antibodies efficiently blocked the interaction of LGI1 with its receptor ADAM22 in vitro and their mean LGI1 signal on mouse brain sections was weak as compared to the remaining, non-ADAM22-competing antibodies. Nevertheless, both types of LGI1 antibodies increased the intrinsic cellular excitability and glutamatergic synaptic transmission of hippocampal CA3 neurons in slice cultures.

The binding of autoantibodies to LGI1 disrupts pre- and postsynaptic LGI1 signaling, resulting in neuronal hyperexcitability (Petit-Pedrol et al, 2018). By blocking the activity of FcRn, rozanolixizumab accelerates the catabolism of antibodies and reduces the concentration of pathogenic IgG, thus offering an alternative to existing treatments. Treatment with rozanolixizumab is expected to result in a decrease in LGI1 autoantibodies and thus to reduce the associated pathological processes and ongoing clinical sequelae.

Current therapeutic approaches for AIE are thought in part to be based on lowering levels of pathogenic autoantibodies, which represents targeted, rational, and effective treatment modalities of autoimmune diseases. Therefore, removal of the IgG autoantibodies by FcRn blockade may provide an effective therapeutic option for IgG autoantibody-mediated autoimmune disorders, in this case for the treatment of LGI1 AIE.

AIE001 is a Phase 2, multicenter, randomized, double-blind, placebo-controlled, 2-arm, repeat-dose study that aims to enroll approximately 68 study participants with LGI1 AIE. To be eligible for inclusion in the study, participants must have disease symptoms onset within 12 months of Screening, be deemed appropriate for initiation or re-initiation of high dose corticosteroids (500 to 1000mg MP equivalent/day) based on clinical symptoms and history, or have initiated high dose corticosteroids within 42 days of randomization, and be seropositive for LGI1 antibodies. Study participants are eligible for inclusion if they are experiencing FBDS (with or without focal [partial] seizures) or focal (partial) seizures including focal to bilateral tonic-clonic seizures, or have experienced such seizure which subsided following initiation of high dose corticosteroids (500 to 1000mg MP equivalent/day).

As described in Section 2.1, the FBDS type is unique to LGI1 AIE; however, patients with LGI1 AIE may also experience focal and tonic-clonic seizures, that are not unique to LGI1 AIE. Therefore, participants eligible via these seizure types must also meet additional criteria for possible AIE, as outlined by Graus et al (2016) in a position paper designed to provide a practical clinical approach to diagnosing AIE. Coupled with this, study participants are excluded if they have previously been diagnosed with epilepsy, have a new-onset seizure that is unrelated to LGI1 AIE, or if there is any known or suspected medical cause for the onset of seizures, other than possible AIE. Therefore, although AIE001 permits the entry of study participants with focal (partial) including focal to bilateral tonic-clonic seizures in the absence of FBDS, these participants must also meet additional criteria designed to reduce the potential risk of enrolling study participants who do not have LGI1 AIE. In this way, AIE001 intends to enroll a study population that reflects the characteristics of the real-world LGI1 AIE population.

At randomization, study participants will be stratified by:

---

- Time from disease symptom onset ( $\leq$ 6 months or  $>$ 6 months from disease symptom onset)
- Cognitive function (RBANS score of  $\leq$ 85 or  $>$ 85)

The decision to stratify based on disease symptom onset and cognitive function is based on data from Thompson et al (2018) who showed in a multivariate regression analysis, that the time to the initiation of immunotherapy, and the presence of cognitive impairment significantly affected the likelihood of FBDS cessation. Factors such as the time to antiepileptic drug administration, age, sex, or the frequency of FBDS were not statistically significant in the model. These findings were supportive of Dubey et al (2017) who showed that early initiation of therapy ( $<$ 6 months from symptom onset) was an independent predictor of favorable seizure outcome. Based on these observations, study participants will be stratified at randomization according to time since disease symptom onset ( $\leq$ 6 months or  $>$ 6 months) and the presence or absence of cognitive impairment.

The stratification by cognitive impairment will be based on the RBANS index score. The RBANS cognitive battery measures performance across a range of cognitive domains (see Section 8.1.2). The RBANS index score reflects an aggregate of performance on these domains, and is computed with reference to age-based normative data derived from a cognitively normal population. In this context, an RBANS index score of 85 reflects a value of 1 standard deviation (SD) below the mean of the age relevant normal population (Duff et al, 2008; Randolph et al, 1998), such that an RBANS index score of  $\leq$ 85 is indicative of clinically important cognitive impairment, while an RBANS index score above 85 can be categorized as cognitively normal. Therefore, to address the extent to which cognitive impairment at baseline may influence the nature and magnitude of response to treatment in AIE001, study participants will be stratified by RBANS score of  $\leq$ 85 or  $>$ 85.

There are currently no approved treatments for any of the AIE conditions. Given this, and the need for appropriately controlled studies to investigate the impact of a new treatment on the symptoms of LGI1 AIE, AIE001 has been designed with a placebo control. In AIE001, all study participants will enter the study having initiated or having been deemed appropriate for initiation or re-initiation of the first-line treatment that will be tapered as per the schedule in Section 1.2. In this way, the study aims to ascertain if rozanolixizumab offers a benefit beyond steroid therapy. The planned treatment duration for AIE001 is 24 weeks. This duration was selected to allow for the steady down-titration of oral steroids, and a sufficient interval for rozanolixizumab to exert a pharmacodynamic effect on IgG levels and the hypothesized therapeutic effect on the symptoms of LGI1 AIE. To ensure that all study participants are receiving appropriate clinical care throughout the duration of the study, participants who do not experience a clinical improvement (ie, an absence of clinical benefit) within the first 4 weeks of the Treatment Period or experience a clinical worsening (ie, a loss of clinical benefit) at any time (Section 7.1.3) or require rescue treatment at any time (Section 6.5.3) must be withdrawn.

#### **4.3 Justification for dose**

The planned dose of rozanolixizumab for this study is [REDACTED] by sc infusion. As outlined below, this dose is justified by:

- Clinical data from the pivotal Phase 3 study (MG0003) showing a meaningful improvement at repeated doses of 7mg/kg and 10mg/kg by body weight tiers in gMG.

- Pharmacodynamic data showing a desired reduction in IgG levels of 70% from Baseline after repeated doses of 7mg/kg and 10mg/kg.
- Simulations from a population PK-PD analysis showing comparable exposure and IgG reduction for a [REDACTED] fixed dose and weight-tiered doses approximating 7mg/kg and 10mg/kg.

Rozanolixizumab has been studied in two Phase 2 studies in gMG and ITP with body weight normalized dosing (mg/kg). Repeated doses up to 10mg/kg and single doses up to 20mg/kg were generally well tolerated with an acceptable safety profile in these Phase 2 studies. In study participants with gMG, clinically relevant improvements in day-to-day functioning were observed following treatment with rozanolixizumab 7mg/kg compared with placebo. In study participants with ITP, rozanolixizumab produced clinically meaningful responses across the treatment groups (rozanolixizumab 4mg/kg to 20mg/kg at varying administration frequency), in all of the response variables defined by platelet counts.

A Phase 3 study, MG0003, has been completed to evaluate the efficacy and safety of rozanolixizumab in study participants with gMG. The dose regimens being evaluated in these studies were weight-tiered doses approximating 7mg/kg and 10mg/kg Q1W.

The proposed [REDACTED] fixed dose of rozanolixizumab is selected to achieve a comparable range of exposures and IgG reductions as the weight-tiered doses that have been evaluated in the completed Phase 3 pivotal study in gMG.

A population PK-PD model was developed based on observed PK and IgG data from the pivotal Phase 3 study (MG0003), two Phase 2 studies (TP0001, MG0002), and two Phase 1 studies (UP0018 and UP0060). Rozanolixizumab exposure and IgG response to rozanolixizumab were comparable between healthy participants and the gMG and ITP populations. In addition, ethnicity was not found to affect PK or IgG response. Therefore, there are no anticipated changes in exposure or IgG responses, where the baseline IgG levels are similar, between different indicated populations or ethnicities.

Simulations performed using the population PK-PD model show that the planned dose of [REDACTED] should:

- Produce PK variability similar to that with weight-tiered dosing.
- Achieve rozanolixizumab exposures that are consistent with those obtained with weight-tiered doses of 7mg/kg and 10mg/kg Q1W as used in the currently ongoing Phase 3 studies.
- Achieve and maintain a desired IgG reduction of 70% from Baseline, irrespective of body weight.

A fixed-dose regimen will simplify the dosing regimen to be more convenient for physicians and patients and to reduce the potential for dosing errors. Thus, a dose regimen of [REDACTED] is planned for investigation in this study.

#### 4.3.1 Justification for IgG target

Rozanolixizumab administration resulted in a rapid clearance of serum IgG levels in both healthy volunteers (UP0018 and UP0060) and patients with gMG (MG0002 and MG0003) or ITP

(TP0001). In MG0003, serum IgG levels decreased reaching a mean maximum reduction of approximatley 71% for the rozanolixizumab  $\approx$ 7mg/kg group and 78% for the  $\approx$ 10mg/kg group. The reduction in IgG was mirrored by a reduction in anti-acetylcholine receptor (AChR) autoantibodies in patients with gMG and demonstrated a █ clinically meaningful improvement in clinical outcome scales (MG-ADL and QMG) compared with placebo.

A rozanolixizumab-induced IgG lowering of about 70% from Baseline is similar to that achieved with other FcRn antagonists and alternative strategies such as PEX, and falls within the range associated with clinical benefit in various autoimmune indications.

For AIE, indication-specific targets for IgG lowering are not yet established. The current assumption is that the desired level of IgG reduction would be similar to those proved to be efficacious in gMG.

#### **4.4 End of study definition**

A study participant is considered to have completed the study if he/she has completed all phases of the study, including the SFU Period. Study participants will have an EOT Visit performed 1 week after the final dose of IMP or upon discontinuation of the study, followed by a SFU phone call 4 weeks after and an EOS Visit 8 weeks after the final dose.

The end of study is defined as the date of the last visit of the last study participant in the study.

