Study participants who complete the 24-week Treatment Period and require further treatment may have the option to access rozanolixizumab via another clinical study or an access program, if available, as per local laws and regulations. Study participants continuing with rozanolixizumab must complete an End of Treatment Visit and be transitioned to rozanolixizumab provided by those alternative options without undergoing SFU or EOS Visits.

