#### **8.3.1 Time period and frequency for collecting AE and SAE information**

All AEs and SAEs will be collected from the signing of the ICF until the EOS Visit at the time points specified in the Schedule of Activities (Section 1.3). In order to ensure complete safety data collection, all AEs occurring during the study (ie, after the signing of the Informed Consent form), including any pretreatment and posttreatment periods required by the protocol, must be reported in the eCRF even if no study medication was taken but specific study procedures were conducted. This includes all AEs not present prior to the initial visit and all AEs that recurred or worsened after the initial visit.

All SAEs will be recorded and reported to the sponsor or designee within 24 hours, as indicated in Appendix 3 (Section 10.3). The investigator will submit any updated SAE data to the sponsor within 24 hours of it being available.

The investigator is specifically requested to collect and report to UCB (or its representative) any SAEs (even if the investigator is certain that they are in no way associated with the study medication), up to 30 days from the end of the study for each participant, and to also inform participants of the need to inform the investigator of any SAE within this period. Serious AEs that the investigator thinks may be associated with the study medication must be reported to UCB regardless of the time between the event and the end of the study.

The method of recording, evaluating, and assessing causality of AE and SAE and the procedures for completing and transmitting SAE reports are provided in Appendix 3 (Section 10.3).

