## **9.4 Planned safety and other analyses**

### **9.4.1 Safety analyses**

All safety analyses will be listed and summarized for the SS.

The frequency and severity of all TEAEs will be presented for each treatment group separately by System Organ Class, high level term, and preferred term (Medical Dictionary for Regulatory Activities). The data will be displayed as number of study participants experiencing the TEAE, percentage of study participants, and number of TEAEs. A TEAE is defined as any event that was not present prior to the first administration of IMP or any unresolved event already present before the first administration of IMP that worsens in intensity following exposure to treatment up to the end of the Treatment Period (Week 25) and including the 8-week SFU.

Laboratory evaluations and vital signs as well as ECG data will be analyzed over time. Possibly clinically significant treatment-emergent abnormalities will be listed and summarized by visit for each treatment group.

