5.1.1.3 Study periods

The maximum study duration per study participant is 38 weeks. There are 3 study periods:

- Screening Period: up to 42 days;
- Treatment Period: 24 weeks;
- Safety Follow-Up Period: 8 weeks.

The following definitions for starting and entering the study periods will be applied:

- **Screening Period** starts at the time of the informed consent date and ends the day before the first dose administration of IMP (i.e. generally the day before Day 1 visit date).
- **Treatment Period** starts on the day of first dose administration of IMP (Day 1) and ends at EOT visit or at EDisc visit for participants withdrawn from the study before Week 24 visit. Participants who are withdrawn from the study during the Treatment Period should complete the assessments outlined for the EOT/EDisc visit and enter the SFU Period.
- **Safety Follow-Up Period** starts with one day after Treatment Period and ends at the final assessments at the EOS visit. Participants who have a completed status in the study termination CRF are considered to have completed the Treatment and SFU Period (i.e. entire study).

Notes:

- The end of the study is defined as the date of the last visit of the last participant in the study.
- Patients should be dosed within 2 days of being randomized.

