- **SFU Period:** a TEAE will be assigned to the SFU Period for the tabulations if the start date of the event is greater than 7 days after the date of the final dose of IMP until 8 weeks following the final dose; events starting later than 8 weeks (56 days) following the final dose of IMP are not considered TEAEs.

In the case of early withdrawal in the Treatment Period, a TEAE will be assigned to the Treatment Period based on the last received IMP plus 168 hours (7 days). Subsequent TEAEs (up to 8 weeks (56 days) post-last dose) will be assigned to the SFU Period.

A TEAE will be counted as a TEAE related to IMP if the response to the question “Relationship to Study Medication” is “Related”. Severe TEAEs are those with CTCAE Grade 3 or above, or those without a CTCAE grading classified as ‘severe’ by the Investigator.

AEs will be presented as “number of participants (percentage of participants) [number of events]”. In this style of output, “[number of events]” will include all cases of an AE including repeat occurrences in individual participants, while “number of participants” will count each participant only once.

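### The SAP's 56-day TEAE window does not stop when a participant moves to post-trial rozanolixizumab, so a serious event on that drug could be counted under placebo

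*Protocol*

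**What the plan says.** **Follow-up and roll-over.** Protocol 4.4 has the "EOT Visit performed 1 week after the final dose of IMP", with a call at 4 weeks and the End of Study (EOS) Visit at 8 weeks after that dose. It ties study completion to the SFU Period: "A study participant is considered to have completed the study if he/she has completed all phases of the study, including the SFU Period". Protocol 4.1, with matching text in the Synopsis, gives treatment completers another route. Those who go on to rozanolixizumab outside the trial must have the End of Treatment (EOT) Visit and then "be transitioned to rozanolixizumab provided by those alternative options without undergoing SFU or EOS Visits". The route is not limited to one arm, and 4.4 carries no exception for it.

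**TEAE window.** Protocol 9.4.1 runs the window "up to the end of the Treatment Period (Week 25) and including the 8-week SFU". SAP 5.6.2.1 turns this into a day count. An event more than 7 days after the final dose goes to the SFU Period, and "events starting later than 8 weeks (56 days) following the final dose of IMP are not considered TEAEs". Neither text says what happens when new rozanolixizumab starts.

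**Study periods in the SAP.** SAP 1.2 describes only the path into SFU. The Study periods section ends SFU at the EOS visit and adds: "Participants who have a completed status in the study termination CRF are considered to have completed the Treatment and SFU Period".

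**Arm and collection.** The SAP section on treatment assignment summarizes safety by randomized group and reallocates only when the treatment given was wrong for the assignment. Protocol 8.3.1 collects adverse events until the EOS Visit and also asks for serious adverse events (SAEs) "up to 30 days from the end of the study for each participant".

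**The concern.** TEAE incidence is the safety secondary endpoint. It is meant to compare what happened on, or shortly after, the two randomized treatments. A participant randomized to placebo who takes up post-trial rozanolixizumab is exposed to active drug while still inside the placebo TEAE window. An event then would be credited to placebo by a stated rule, not merely by a gap in the text.

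There is also an opposite problem. A roll-over participant has neither the SFU call nor the EOS Visit, so non-serious events after EOT may never reach the database. The window stays nominally open for 56 days while observation after EOT is incomplete.

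The completion line in the SAP adds a smaller difficulty. If a roll-over participant's termination form says completed, the SAP credits an SFU that did not take place. SAP 6.1.7.1.2 also uses the end of study visit date of completed participants to impute unknown adverse event stop dates, and these participants have no such visit.

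**Working it through.** **1. The plan's own figures.** 8 × 7 = 56 days, as the SAP states. Screening, treatment and follow-up give 42/7 + 24 + 8 = 38 weeks, matching the stated maximum duration.

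**2. Calendar.** The input is a weekly schedule over 24 weeks (interval 7 ± 2 days in the footnotes to Protocol Table 1-1), taken at its nominal days.

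- Final dose: 1 + 23 × 7 = Day 162. The SAP's post-dose PK Days 164 and 166 fit this (162 + 2 and 162 + 4).
- EOT: 162 + 7 = Day 169.
- End of TEAE window: 162 + 56 = Day 218.
- Window left after EOT: 218 − 169 = 49 days, and 49/218 = 22.5% of Day 1 to Day 218.

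**3. SAE request.** The documents do not say when a roll-over participant's own study ends. If that is taken as EOT, the request runs to 169 + 30 = Day 199. That is 199 − 162 = 37 days after the final dose, inside the 56-day window.

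**4. Time on post-trial drug.** The start day is not in the documents. Let it be *s* days after EOT (assumed values).

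| *s* | Days after final study dose before post-trial drug (7 + *s*) | Window days on post-trial drug (49 − *s*) | Days of SAE request on post-trial drug (30 − *s*) |
|---|---|---|---|
| 0 | 7 | 49 | 30 |
| 7 | 14 | 42 | 23 |
| 14 | 21 | 35 | 16 |
| 28 | 35 | 21 | 2 |

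**5. One case through the rules.** A participant randomized to placebo receives placebo throughout, has EOT on Day 169, starts post-trial rozanolixizumab and has an SAE on Day 199.

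- Timing: 37 days after the final dose is more than 7 and not more than 56, so this is an SFU-period TEAE.
- Capture: Day 199 is the last day of the SAE request, so the event is reported.
- Arm: planned post-trial access is not described as incorrect treatment, so reallocation is not triggered. SAP 4.3 also refers to treatment actually received, but in this trial that was placebo.

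The event lands in the placebo column.

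**6. Size of one event.** The SAP reports 12 participants. The split by arm is not given; assume 6 and 6. One additional participant with a TEAE moves that arm by 1/6 = 16.7 points, rounded to 17. SAP 5.6.2.1 counts each participant once, so this needs a participant with no earlier TEAE.

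**The case against.** **Reach.** The roll-over text came with Amendment 6, dated 18 July 2023. The SAP Introduction says nobody was randomized under an amendment that it does not number but that appears to be Amendment 6. SAP Section 5 places all 12 participants under earlier versions. This stands, and it is the main reason for a low priority. It does not close the matter, because roll-over opens at the end of treatment. Someone first dosed on 31 January 2023 reaches Day 169, 168 days later, on 18 July 2023. Recruitment was suspended only on 29 November 2023.

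**Capture and containment.** Post-EOT events reach the database mainly as SAEs. The day rule places those later than day 7 in the SFU Period, outside the Treatment Period tabulation, and all adverse events are listed. With 12 participants each case could be checked by hand. All of this stands, but a listing does not change the count in the summary table.

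**Wording of the definition.** The general TEAE definition includes the 8-week SFU and could be read as needing an SFU that was actually entered. The period-assignment rule, which a programmer would follow, counts days from the final dose and makes no such test.

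**Completion.** A reader might infer that 4.4 and 4.1 contradict each other outright. They need not: a roll-over participant can complete treatment without completing the study. SAP 5.2 tabulates the two separately, and no analysis set depends on completion. What remains is the SAP line that equates completed status with SFU done.

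**Unequal follow-up.** A reader might also infer that incidence is presented as if everyone were followed equally. SAP 5.6.2.2 plans TEAEs per 100 patient-years, so that goes too far. The end of risk time for that summary is, however, not defined.

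**Conclusion.** The point holds in a limited form, as a minor matter. As written, the TEAE rule would place an SAE on post-trial rozanolixizumab under placebo if the participant had been randomized to placebo. Non-serious events after EOT may be missed in roll-over participants of either arm.

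The size depends on three assumptions: nominal weekly dosing, a participant's study end taken as EOT, and a post-trial start 0 to 28 days after EOT. On these, 49 down to 21 window days, and 30 down to 2 days of the SAE request, fall on post-trial drug. The shift of up to 17 points per event further assumes six per arm and no earlier TEAE in that participant.

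Two stronger readings are not supported. One is that placebo incidence is in fact contaminated: the documents do not say that anyone rolled over, and the number may be zero. The other is that a roll-over participant has no more than 7 of the 56 post-dose days free of post-trial drug. Transition follows EOT, so 7 days is the minimum on the nominal schedule; the true figure depends on an unstated start date.

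**What to change.** - **SAP 5.6.2.1:** end the TEAE window at the earlier of 56 days after the final study dose and the day before the first post-trial rozanolixizumab dose. List later events separately.
- **SAP 5.6.2.2:** use the same end date as the end of risk time for TEAEs per 100 patient-years.
- **SAP Study periods and 5.2:** do not treat roll-over participants as having completed the SFU Period. Show them in disposition as having completed treatment and rolled over.
- **Protocol 4.4:** reconcile it with 4.1 by stating the completion status of roll-over participants and when their adverse event collection ends.

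The cost is one date field, for the first post-trial dose, and minor wording. If nobody rolled over, a sentence in the SAP saying so would settle the analysis side. No clinical rule changes.
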